4.1.4. Last Available Value

The last available value is the last nonmissing measurement obtained after starting ruxolitinib cream or vehicle cream and within 30 days after the last application of ruxolitinib cream or vehicle cream, or before the first application of ruxolitinib cream in the next period, whichever is earlier.

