8.1. General Considerations

The analyses in this section will be provided for the safety population in the VC and LTS periods. Summary tables may be replaced with listings when appropriate. For instance, an AE frequency table may be replaced with a listing if it only contains a few unique PTs reported on relatively few participants.

Unless otherwise stated, table summaries will be limited to AEs occurring within 30 days of the last application of study drug or the first application in the LTS period (if available) of the study, whichever is earlier.

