8.2. Adverse Events

8.2.1. Adverse Event Definitions

A TEAE is any AE either reported for the first time or worsening of a pre-existing event after first administration of study drug. Analysis of AEs (as discussed below) will be limited to TEAEs, but data listings will include all AEs regardless of their timing in relation to study drug administration.

Adverse events will be tabulated by MedDRA PT and SOC. Severity of AEs will be graded using the NCI CTCAE. The CTCAE v4.03 is used for this study. The CTCAE reporting guidelines and grading details are available on the Cancer Therapy Evaluation Program website.

The subset of AEs considered by the investigator to be related to study drug will be considered to be treatment-related AEs. If the investigator does not specify the relationship of the AE to study drug, the AE will be considered to be treatment-related. The incidence of AEs and treatment-related AEs will be tabulated. Serious AEs will also be tabulated.

Any missing onset date, causality, or severity must be queried for resolution. Unresolved missing causality and severity will be handled according to the following rules:

- An unresolved missing causality will be considered treatment-related.
- An unresolved missing severity will be identified as an unknown severity.

For purposes of analysis, all AEs will be considered TEAEs unless the AE can unequivocally be defined as not treatment-emergent.

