2.11.2	Summary of Participants in Each Category of PGIC Score in VC Period	ITT
2.11.3	Summary of PGIC Score in VC Period	ITT

Table No.	Title	Population
EQ-5D-5L		
2.12.1	Summary and Analysis of EQ VAS Score From Baseline to Week 52	ITT
2.12.2	Summary of EQ VAS Score in LTS Period	ITT
WPAI-SHP		
2.13.1.1	Summary and Analysis of WPAI-SHP v2.0 Score From Baseline to Week 52	ITT
2.13.1.2	Summary of WPAI-SHP v2.0 Score in LTS Period	ITT
Exposure, Adverse Events, Laboratory, and Vital Signs		
Exposure		
3.1.1.1	Summary of Exposure in VC Period	Safety
3.1.1.2	Summary of Exposure From Baseline to Week 52	Safety
3.1.1.3	Summary of Exposure in LTS Period	Safety
3.1.2	Summary of Study Drug Compliance in VC Period	Safety
Adverse Events		
3.2.1.1	Overall Summary of Treatment-Emergent Adverse Events in VC Period	Safety
3.2.1.1.1	Overall Summary of Treatment-Emergent Adverse Events by Age Group in VC Period	Safety
3.2.1.2	Overall Summary of Treatment-Emergent Adverse Events From Baseline to Week 52	Safety
3.2.1.2.1	Overall Summary of Treatment-Emergent Adverse Events by Age Group From Baseline to Week 52	Safety
3.2.1.3	Overall Summary of Treatment-Emergent Adverse Events in LTS Period	Safety
3.2.2.1	Summary of Treatment-Emergent Adverse Events by MedDRA System Organ Class and Preferred Term in VC Period	Safety
3.2.2.1.1	Summary of Treatment-Emergent Adverse Events by MedDRA System Organ Class and Preferred Term by Age Group in VC Period	Safety
3.2.2.2	Summary of Treatment-Emergent Adverse Events by MedDRA System Organ Class and Preferred Term From Baseline to Week 52	Safety
3.2.2.2.1	Summary of Treatment-Emergent Adverse Events by MedDRA System Organ Class and Preferred Term by Age Group From Baseline to Week 52	Safety
3.2.2.3	Summary of Treatment-Emergent Adverse Events by MedDRA System Organ Class and Preferred Term in LTS Period	Safety
3.2.3.1	Summary of Treatment-Emergent Adverse Events by MedDRA Preferred Term in Decreasing Order of Frequency in VC Period	Safety
3.2.3.1.1	Summary of Treatment-Emergent Adverse Events by MedDRA Preferred Term in Decreasing Order of Frequency by Age Group in VC Period	Safety
3.2.3.2	Summary of Treatment-Emergent Adverse Events by MedDRA Preferred Term in Decreasing Order of Frequency From Baseline to Week 52	Safety
3.2.3.2.1	Summary of Treatment-Emergent Adverse Events by MedDRA Preferred Term in Decreasing Order of Frequency by Age Group From Baseline to Week 52	Safety

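### The SAP's one stated adverse event window suits only the vehicle-controlled tables; none is stated for the LTS or Week 0–52 tables

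*SAP*

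**What the plan says.** SAP 8.1 opens with its scope: "The analyses in this section will be provided for the safety population in the VC and LTS periods". It then gives one AE window for tables, with two anchors. The first anchor, with its opening proviso, reads: "Unless otherwise stated, table summaries will be limited to AEs occurring within 30 days of the last application of study drug". The second anchor, in the same sentence, reads: "or the first application in the LTS period (if available) of the study, whichever is earlier".

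SAP 8.2.1 defines treatment emergence by a start only: "A TEAE is any AE either reported for the first time or worsening of a pre-existing event after first administration of study drug". It gives no end date by period, and it keeps every AE in the listings whatever the timing. SAP 8.2.2 lists the summaries and adds no window.

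Appendix A plans the AE tables in three sets, all on the safety population. The overall summaries are:

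- Table 3.2.1.1: "Overall Summary of Treatment-Emergent Adverse Events in VC Period"
- Table 3.2.1.2: "Overall Summary of Treatment-Emergent Adverse Events From Baseline to Week 52"
- Table 3.2.1.3: "Overall Summary of Treatment-Emergent Adverse Events in LTS Period"

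On treatment groups, SAP 5.2 names three for the VC period and four for the LTS period, with the two vehicle-to-active sequences separate. It names none for Week 0–52. SAP 5.3.3 groups the safety population by the treatment actually applied on Day 1. SAP 10.1 drops the LTS evaluable population and moves LTS safety to the safety population.

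**The concern.** A window that closes when LTS treatment starts cannot serve a table about LTS treatment, yet it is the only window written for a section that covers both periods.

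Collecting longer-term safety data on intermittent use is a stated purpose of the LTS period (Protocol 2.3.1), and the SAP also governs the sister study 304 (SAP 1), so the gap affects two trials.

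The two affected table sets would fail differently. An empty LTS table would be noticed at once. A Week 0–52 table would still be filled, with VC events, so the same error there need not show itself.

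If programmers override the default, they must choose the end date, the handling of events that straddle Week 8, and the column for events of former vehicle participants. SAP 9 unblinds the sponsor after the primary database lock, so unless these choices are written down first they could be made with treatment codes known.

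**Working it through.** The plan states no figure here, so there is none to reproduce. The check applies the date rule and then looks for another rule that would replace it.

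**Inputs**

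- Two anchors, last application (LA) and first LTS application (L1): SAP 8.1.
- VC treatment 8 weeks, LTS treatment 44 weeks: Protocol 4.2.
- Week 8 visit window ±3 days: Protocol Table 3.
- Assumed nominal days, for illustration: L1 = 8 × 7 + 1 = Day 57 (Day 54 to 60 with the visit window); LA = 52 × 7 = Day 364.

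**Step 1. The rule as most naturally read.** Cutoff = min(LA + 30, L1).

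- Participant who does not enter the LTS period: cutoff = LA + 30, a sensible VC window.
- Participant who enters: LA ≥ L1 by definition, so LA + 30 > L1 and the cutoff is always L1.
- With numbers: min(364 + 30, 57) = min(394, 57) = Day 57. For LA = 57, 60 or 100, min(87, 57), min(90, 57) and min(130, 57) all give Day 57.

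**Step 2. Effect on each table set.**

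- VC tables: correct.
- LTS tables: the period of interest runs from Day 57 to Day 394, which is 394 − 57 + 1 = 338 days. Nothing after L1 is kept, except possibly events dated on that day.
- Week 0–52 tables: 56 of 394 days are covered, 56/394 = 14% (53/394 = 13% to 59/394 = 15% across the visit window). The content would repeat the VC tables.

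**Step 3. The other grammatical reading.** If the 30 days apply to both anchors, cutoff = min(LA, L1) + 30 = 57 + 30 = Day 87. That keeps 87 − 57 + 1 = 31 of 338 LTS days, 31/338 = 9%. It would also run the VC tables 30 days into LTS treatment, which counts against it. The parallel rule for measurements in SAP 4.1.4 also favours Step 1, since it cuts at 30 days "or before the first application of ruxolitinib cream in the next period, whichever is earlier".

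**Step 4. Is another AE window stated?**

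| Place | Start | End |
|---|---|---|
| SAP 8.1 | none given | earlier of LA + 30 and L1 |
| SAP 8.2.1 | first administration of study drug | none |
| SAP 8.2.2 | none | none |
| Appendix A titles | period named | period named, no dates or tail |

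No section supplies dates for the LTS or Week 0–52 tables.

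**Step 5. Attribution.** About 600 × 1/5 = 120 participants start on vehicle. If LTS events are kept in the Week 0–52 tables and SAP 5.3.3 is followed, events on active cream in these participants are counted under vehicle.

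**The case against.** The strongest reply is that the rule announces itself as a default that yields where the SAP says otherwise, and the SAP arguably does. The scope sentence of 8.1 includes the LTS period, the Appendix A titles name the periods, SAP 5.2 defines LTS groups, and SAP 10.1 says that LTS safety will be evaluated. Conventions elsewhere are set by period: Day 1 (4.1.1), the crossover baseline (4.1.3), the last available value (4.1.4) and treatment duration (6.4). On this view the sentence is a VC cutoff, loosely worded. Appendix A also refers to standard safety table conventions that are not available here and may define a window. Finally, the AE tables are descriptive and lie outside the type I error procedure.

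Most of this stands as evidence of intent. A reader might infer that the plan discards every LTS event, which is 44 of 52 treatment weeks (44/52 = 85%), or about 600 × 44/52.18 = 506 person-years. The documents do not support that inference. The figures describe only the literal worst case, and the person-years also require all 600 participants to enter and complete the LTS period. The second reading keeps about 30 days, and the listings keep every AE.

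The reply does not supply the missing rule. A title names a period but does not say whether the 30-day tail belongs to it, whether an event that began before Week 8 counts, or which column a vehicle starter's event goes in. Appendix A itself calls its list a guideline.

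**Conclusion.** The point holds in a limited form. The only AE tabulation window stated in the SAP is correct for the VC tables and wrong for the other two planned sets. Applied to them, it removes all LTS events, or about 91% of LTS days on the reading that keeps the first 30 days or so (307 of 338). The result that the cutoff falls at L1 needs no assumption beyond entry into the LTS period. The day counts rest on the nominal timeline above.

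The realistic harm is smaller than the literal one. An empty LTS table would be caught, no hypothesis test is affected, and no event leaves the report. What remains is a Week 0–52 table set that could be wrong without looking wrong, plus unstated choices about end date, carry-over and vehicle starters. The statement that no other window exists is limited to the SAP text available; the separate table conventions were not seen.

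**What to change.** Amend SAP 8.1, with a matching line in 5.2 or 5.3.3:

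- **VC tables.** Limit the present rule to these: Day 1 to the earlier of 30 days after last VC application and first LTS application. Say which table takes an event dated on the day of first LTS application.
- **LTS tables.** First LTS application to 30 days after last application, by the four LTS groups in SAP 5.2.
- **Week 0–52 tables.** Day 1 to 30 days after last application. Attribute vehicle starters' events by treatment at onset, not by Day 1 treatment.
- **Carry-over.** An event that started in the VC period counts in LTS tables only if it worsens after first LTS application.
- **Gaps in treatment.** LTS treatment is intermittent (Protocol 4.1), so say that last application means the last one in the study, and how events more than 30 days after it are shown for participants still attending visits.

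The cost is a few SAP sentences and the matching programming specifications, with no change to conduct or data collection. The change should be dated before the sponsor is unblinded at the primary database lock. If that has passed, it should be recorded in SAP 10.2 as made afterwards.

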8.2. Adverse Events

8.2.1. Adverse Event Definitions

A TEAE is any AE either reported for the first time or worsening of a pre-existing event after first administration of study drug. Analysis of AEs (as discussed below) will be limited to TEAEs, but data listings will include all AEs regardless of their timing in relation to study drug administration.

Adverse events will be tabulated by MedDRA PT and SOC. Severity of AEs will be graded using the NCI CTCAE. The CTCAE v4.03 is used for this study. The CTCAE reporting guidelines and grading details are available on the Cancer Therapy Evaluation Program website.

The subset of AEs considered by the investigator to be related to study drug will be considered to be treatment-related AEs. If the investigator does not specify the relationship of the AE to study drug, the AE will be considered to be treatment-related. The incidence of AEs and treatment-related AEs will be tabulated. Serious AEs will also be tabulated.

Any missing onset date, causality, or severity must be queried for resolution. Unresolved missing causality and severity will be handled according to the following rules:

- An unresolved missing causality will be considered treatment-related.
- An unresolved missing severity will be identified as an unknown severity.

For purposes of analysis, all AEs will be considered TEAEs unless the AE can unequivocally be defined as not treatment-emergent.

8.2.2. Adverse Event Summaries

An overall summary of AEs by treatment group will include:

- Number (%) of participants reporting any TEAEs
- Number (%) of participants reporting any serious TEAEs
- Number (%) of participants reporting any Grade 3 or higher TEAEs
- Number (%) of participants reporting any treatment-related TEAEs
- Number (%) of participants who temporarily interrupted study drug because of TEAEs
- Number (%) of participants who permanently discontinued study drug because of TEAEs
- Number (%) of participants who had a fatal TEAE

The following summaries will be produced by MedDRA term (if 2 or fewer participants appear in a table, a listing may be appropriate):

- Summary of TEAEs by SOC and PT
- Summary of TEAEs by PT in decreasing order of frequency
- Summary of Grade 3 or higher AEs by SOC and PT
- Summary of Grade 3 or higher AEs by PT in decreasing order of frequency
- Summary of serious TEAEs by SOC and PT
- Summary of serious TEAEs by PT in decreasing order of frequency
- Summary of treatment-related TEAEs by SOC and PT
- Summary of treatment-related TEAEs by PT in decreasing order of frequency

- Summary of Grade 3 or higher treatment-related TEAEs by SOC and PT
- Summary of treatment-related serious TEAEs by SOC and PT
- Summary of TEAEs with a fatal outcome by SOC and PT
- Summary of TEAEs leading to dose interruption of study drug by SOC and PT
- Summary of TEAEs leading to discontinuation of study drug by SOC and PT
- Summary of TEAEs requiring concomitant medications by SOC and PT

Subgroup analysis for TEAEs by age categories will also be provided.

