4.2. Overall Study Duration

Participants will be on study for a duration of up to 60 weeks (28 days screening, 8 weeks of treatment in the VC period, 44 weeks of treatment in the LTS period, and a 30 (+ 7)-day safety follow-up; see [Figure 1](#)).

The study will begin when the first participant (or parent or guardian) signs the ICF (and if needed, an assent form). The end of the study is defined as the date of the last visit of the last participant in the study or discontinued study drug and have completed applicable follow-up assessments.

A participant is considered to have completed the study if he/she has completed all study visits, including the follow-up visit.

The investigator will be expected to monitor for and report any SAEs and pregnancies, as detailed in [Section 9](#). The remaining participants are considered to be on study until a discontinuation criterion is met and written notification is provided to the sponsor.

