7. DISCONTINUATION OF STUDY TREATMENT AND PARTICIPANT DISCONTINUATION/WITHDRAWAL

7.1. Discontinuation of Study Treatment

7.1.1. Reasons for Discontinuation

Participants **must** be discontinued from study treatment for the following reasons:

- Due to lack of efficacy response during the LTS (defined as no change/improvement in either %BSA or IGA when treated continuously for 8 weeks).

- The participant becomes pregnant.

- Consent is withdrawn.

Note: Consent withdrawn means that the participant has explicitly indicated that they do not want to be followed any longer; in this case no further data, except data in public domain, may be solicited from or collected on the participant. Participants may choose to discontinue study treatment and remain in the study to be followed for progression and survival.

- Further participation would be injurious to the participant's health or well-being, in the investigator's medical judgment.

- Any adverse event of unacceptable severity as noted in Section [6.5.2](#).

- The study is terminated by the sponsor.

- The study is terminated by the local health authority, IRB, or IEC.

A participant **may** be discontinued from study treatment as follows:

- If, at 2 consecutive study visits, a participant's drug usage exceeds one 60 g tube per 4 days. The medical monitor should be consulted for instruction on handling the participant.

- If, during the course of the study, a participant is found not to have met eligibility criteria, the medical monitor, in collaboration with the investigator, will determine whether the participant should be withdrawn from study treatment.

- If a participant is noncompliant with study procedures or study drug/treatment administration in the investigator's opinion, the medical monitor should be consulted for instruction on handling the participant.

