4.1.3. Baseline Value

Baseline is the last nonmissing measurement obtained before or on the day of first application of ruxolitinib cream or vehicle cream.

For participants who cross-over treatment in LTS period, baseline is the last nonmissing measurement obtained before or on the day of first application of study treatment in LTS period.

For randomized participants not treated with any study drug, baseline is defined as the last nonmissing assessment before or on the day of randomization for all parameters.

When scheduled assessments and unscheduled assessments occur on the same day and time of the assessment or time of first application is not available, use the following convention to determine baseline:

- If both a scheduled and an unscheduled visit are available on the day of the first application and the time is missing, use the scheduled assessment as baseline.
- If all scheduled assessments are missing on the day of the first application and an unscheduled assessment is available, use the unscheduled assessment as baseline.

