5.2. Treatment Groups

This is a randomized, double-blinded vehicle-controlled study followed by a LTS extension period. Data will be summarized based on treatment regimen that was assigned (ITT) or that the participant actually applied (safety).

During the VC period, the treatment groups will be 1.5% BID, 0.75% BID, and Vehicle.

During the LTS period, the treatment groups will be 1.5% BID, 0.75% BID, Vehicle to 1.5% BID, and Vehicle to 0.75% BID.

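### Long-term adverse events are planned only as crude percentages although time at risk can differ between groups; add exposure-adjusted rates and define the denominators

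*SAP*

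**What the plan says.** SAP 8.2.2 lists the overall adverse event summary as participant counts with percentages, beginning with "Number (%) of participants reporting any TEAEs", followed by tables by system organ class and preferred term. SAP 8.2.1 adds that "The incidence of AEs and treatment-related AEs will be tabulated" but defines no person-time denominator. Appendix A carries the tables into two long-term displays, "Overall Summary of Treatment-Emergent Adverse Events From Baseline to Week 52" and "Overall Summary of Treatment-Emergent Adverse Events in LTS Period". Neither SAP section 8, the Appendix A titles nor Protocol 10.4.3 mentions an exposure-adjusted rate or a time-to-event analysis of adverse events.

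Planned time is "8 weeks of treatment in the VC period, 44 weeks of treatment in the LTS period" (Protocol 4.2). SAP 5.2 gives the long-term columns: "During the LTS period, the treatment groups will be 1.5% BID, 0.75% BID, Vehicle to 1.5% BID, and Vehicle to 0.75% BID". It does not give the columns of the Baseline to Week 52 tables. For crossovers, SAP 4.1.3 resets the reference point: "baseline is the last nonmissing measurement obtained before or on the day of first application of study treatment in LTS period".

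Four other provisions matter:

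- SAP 10.1 drops the protocol's LTS evaluable population and uses the safety population for LTS safety. SAP 5.3.3 defines that population as everyone with at least one application of study cream.
- SAP 8.1 ends the default event window 30 days after last application or at the first LTS application, whichever is earlier, unless stated otherwise.
- SAP 9 schedules an analysis once about 200 participants across the two sister studies have 12 months of treatment.
- Protocol 7.1.1 lists, among the reasons for which study treatment must stop, "Due to lack of efficacy response during the LTS".

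**The concern.** A crude percentage rises with the time a participant is observed. If two columns have different time at risk, their percentages differ even when the underlying event rates are the same. Long-term safety under intermittent use is a stated purpose of the 44-week extension (Protocol 2.3.1), so these tables will be read across columns. The plan leaves four routes to unequal time:

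- **By design.** Up to 52 weeks on ruxolitinib for those randomized to it, against at most 44 weeks for vehicle crossovers.
- **By denominator.** Read literally, the LTS tables may keep in the 1.5% and 0.75% columns safety-population participants who never entered the LTS. The two crossover columns can hold only people assigned to ruxolitinib at Week 8.
- **By data cut.** At the 12-month cut many participants will still be in follow-up, so a percentage has no fixed time base.
- **By attrition.** The mandatory stop for lack of efficacy could remove more participants from one dose than the other.

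A column with less time at risk would look safer than it is.

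**Working it through.** **The plan's own figure.** The only quantitative design figure is power above 95% (Protocol 10.1). With 600 randomized 2:2:1 (240, 240, 120), a two-sided Fisher exact test at 0.025 gives 98.9% for 30% against 10%, and above 99.9% for 45% against 10%. The claim reproduces, but it concerns efficacy. The documents state no adverse event rate, LTS dropout rate or safety precision, so those inputs below are assumptions shown over a range.

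**Step 1: 52 against 44 weeks, same true rate.** Crude proportion = 1 − exp(−λt), where λ is the rate per week (a person-year taken as 52 weeks) and t is weeks at risk.

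| Rate per 100 person-years (assumed) | 44 weeks | 52 weeks | Ratio |
|---|---|---|---|
| 5 | 4.1% | 4.9% | 1.18 |
| 20 | 15.6% | 18.1% | 1.16 |
| 50 | 34.5% | 39.3% | 1.14 |
| 100 | 57.1% | 63.2% | 1.11 |

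**Step 2: the two doses within the LTS.** All groups have the same planned 44 weeks. Let a proportion d drop out at a constant hazard μ = −ln(1 − d)/44. Then crude proportion = [λ/(λ + μ)] × [1 − exp(−44(λ + μ))], and mean weeks under observation = d/μ.

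At 20 per 100 person-years, λ = 0.20/52 = 0.003846 per week.

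- d = 10%: μ = 0.002395, mean 41.8 weeks, crude 14.8%.
- d = 20%: mean 39.4 weeks, crude 14.0%.
- d = 30%: μ = 0.008106, mean 37.0 weeks, crude 13.2%.

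Over rates of 5 to 100 per 100 person-years, the ratio of crude percentages is 1.00 with equal dropout, 1.05 to 1.06 for 10% against 20%, and 1.11 to 1.13 for 10% against 30%.

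**Step 3: non-entrants in the LTS denominator.** If a fraction q of a column never entered the LTS, its crude percentage is multiplied by (1 − q) at any event rate. The only discontinuation figure in the documents is 46 of 307, or 15.0%, over 8 weeks in the Phase 2 study (Protocol 2.2.2.4.1). Taking q = 15% as an assumption, 15.6% becomes 0.85 × 15.6% = 13.3%. With q = 5% it becomes 0.95 × 15.6% = 14.8%.

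**Step 4: does a rate repair this?** Mean time to first event or dropout is [1 − exp(−44(λ + μ))]/(λ + μ). Dividing the crude proportion by it returns λ exactly. At 20 per 100 person-years this is 0.148 over 38.5 weeks for d = 10% and 0.132 over 34.2 weeks for d = 30%. Both give 20 per 100 person-years, so the ratio is 1.00. Non-entrants add no events and no time. This holds under a constant hazard with dropout unrelated to event risk.

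**The case against.** The strongest reply is that planned follow-up is balanced where the randomized comparison lies. Both doses have the same 8 plus 44 weeks and the same visits, and all four groups have the same planned 44 weeks within the LTS. This stands. A reader might infer that follow-up differs by dose and that the long-term dose comparison is therefore confounded. The documents do not say so. Protocol 7.1.1 makes differential attrition plausible, given assumed Week 8 response of 45% and 30%, but nothing says how many participants would meet the stopping rule on either dose. LTS use is as needed, so a less effective dose could also mean more days on drug.

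A reader might also infer that a planned table sets 8 weeks of vehicle beside 52 weeks of ruxolitinib, which at 20 per 100 person-years would show 3.0% against 18.1%. No described table is shown to do this. The vehicle-controlled tables compare 8 weeks with 8, and the Baseline to Week 52 columns are undefined. If vehicle starters keep one column throughout, they too have 52 weeks on study. The fault would then be mixed treatments, which a single rate per column would not cure.

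Uneven follow-up at the 12-month cut comes largely from staggered entry, which randomization should balance between doses. It affects the meaning of the absolute percentages more than the contrast.

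Finally, the adverse event outputs are descriptive with no planned test. Exposure is tabulated for the same periods (Tables 3.1.1.1 to 3.1.1.3), and LTS discontinuation is summarized with reasons (SAP 6.2), so an attentive reader could see imbalance. The standard safety table conventions and shells are separate documents, not available here. These points limit the seriousness. They do not supply a rate, an LTS denominator or column definitions.

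**Conclusion.** The point holds as a gap in long-term safety reporting. Unequal time on active drug is built in (52 against at most 44 weeks) and, at equal true rates, is worth a crude ratio of 1.11 to 1.18 wherever those two groups are compared. The LTS denominator is open to a reading that dilutes the 1.5% and 0.75% columns; at an assumed 15% non-entry the crude figure would be 0.85 of its proper value. Distortion between the two doses within the LTS is a risk, not an established fact: none with equal dropout, about 1.05 to 1.13 at 10% against 20% to 30%. Event rates, dropout and non-entry are assumptions, and the calculations take hazards as constant. The efficacy analyses and the 8-week safety comparison are not affected. This is a worthwhile, inexpensive improvement that should be made before the long-term tables are produced.

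**What to change.** Keep n (%) and amend SAP 8.1, 8.2.2, 5.2 and the Appendix A titles as follows:

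1. In the LTS and Baseline to Week 52 overall, serious, Grade 3 or higher and preferred-term tables, add participants with a first event per 100 person-years at risk, with 95% CI.
2. Define person-time as time on study in the period, up to the first event or the end of the event window. Give time on drug as a supplement; the SAP 6.4 duration runs from first to last application and so includes off-treatment gaps.
3. Restrict LTS denominators to participants who applied study drug in the LTS.
4. Define the Baseline to Week 52 columns and state their event window, so that vehicle time and vehicle events stop at the first ruxolitinib application. The default window in SAP 8.1 already ends there for the vehicle-controlled period, but taken literally it would also cut off the Week 52 tables for everyone.

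The cost is a few extra columns and short definitions; application dates are already used for SAP 6.4. Rates assume a roughly constant hazard, which is why n (%) should stay beside them. They also do not correct for dropout related to event risk, so they should be read with the LTS discontinuation reasons by group.
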